Therapeutic Intervention

Patients in the intervention arms will receive two doses of either 10 mg dexamethasone or 20 mg dexamethasone. The first dose will be administered preoperatively within three hours of surgery once the patient receives anesthesia. The second dose will be administered eight hours after the first dose in the inpatient setting by the nurse in that unit. The second dose will be administered using a piggyback setup. Patients in the placebo arm will receive two doses of saline/placebo.

This particular dosing is chosen based on available literature that suggests a safe and effective dose is between 4 and 20 mg of dexamethasone²⁵⁻²⁶.

The administration of either steroid or placebo will occur in a double-blinded fashion. For each study participant, two blinded doses will be sent over from Emory's Investigational Drug Service (IDS). Thus, neither the patient receiving the medication nor the health care professional administering the medication or collecting study outcome data will be aware of whether or not the patient received the steroid or the placebo.

Both the intervention and control groups will receive spinal anesthesia using lidocaine and a standard multimodal postoperative pain management regimen typically used for total knee arthroplasty. This regimen will be standardized across all three attending surgeons participating in the study. The standard multimodal pain management regimen will be as follows:

- Preoperative:
 - **Decadron: 10 or 20mg IV x 2 doses, 8 hours apart (if randomized to study group)**
- Intraoperative:
 - **Ropivacaine:** Given intraoperatively. Injection, subcutaneous tissue/skin. Administered in standard fashion. (300mg)
 - **Toradol:** 30mg q 6hr for 6 total doses. 1st dose given intraoperatively at incision. (15 mg if patient is >65 years of age. Patients with Cr >1.5 will not receive Toradol).
- Postoperative
 - **Tylenol:** 1000mg po q 8hr (scheduled)
 - **Oxycodone:** 5mg or 10mg q 3-4hr prn pain, If intolerant to Oxycodone: second agent line is Hydrocodone or Oral Dilaudid (Tylenol will be adjusted accordingly if patient receives Hydrocodone).
 - **IV Morphine (or Dilaudid):** 1 or 2 mg q 2hr prn breakthrough pain
 - **Morphine PCA:** only for failure of the above
 - **MS Contin:** 15 mg BID for two weeks

On postoperative day (POD) 1, patients will be transitioned to oral (PO) and intravenous (IV) medications on an as-needed basis with a regimen that will be standardized across all study participants.

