
Data Collection

Data will be collected by a number of different health professionals during enrollment, during the patient's postoperative hospital stay, by smart device application (app), and during the patient's routine postoperative follow up visits (1 month, 4 months, and 12 months). After surgery, no participants in any group will be subjected to any extra invasive tests or interventions related to their involvement in the study. Patients will not be informed whether or not they have received the study

drug until after all data collection is complete. The schedule of study activities and data collection are shown in Table 1.

1. **Pain assessment:** Postoperative pain will be assessed using the well-standardized and accepted visual analog pain scale. This data will be recorded at baseline, during the hospital stay, and at all follow-up visits. A smart device app will be used to record this information for the 7-day postoperative period. Questions will be asked morning, afternoon, and evening for every patient. Patients enter alarms for morning, afternoon, and evening the first time they use the app. Patients can later adjust these alarms if necessary. Timestamps will be recorded for each of these entries as patients will be asked about their 'average' pain over the preceding 4 hours, and they will be able to edit/modify prior entries at any time. Patients will also be asked during the first entry for the day if they were awoken from pain or nausea during the previous night, and if they click yes, they will be prompted to select pain scores corresponding to this event. There will be a comments section to provide patients the ability to enter text. Furthermore, during the hospital stay this data will be recorded with each vital sign assessment by the nursing per standard of care. The following scale will be used to assess pain:

[figure not shown]
©1983 Wong-Baker FACES® Foundation. www.WongBakerFACES.org
Used with permission.

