7. **Blood Glucose Levels:** The patient's blood glucose level will be recorded once preoperatively at the pre-anesthesia clinic visit several days before surgery, at POD 1 and at each subsequent in-hospital POD using a hemocue. These do not consist of extra blood tests, as blood draws at these time points are considered standard of care. This data is being collected because hyperglycemia is a potential complication of IV steroid use. If patients experience ketoacidosis or hyperglycemia greater than 300, the study drug/placebo will be discontinued.
8. **Functionality scores:** The Short Form (SF) – 12 and Knee Injury and Osteoarthritis Outcome Score Short Form (KOOS, Jr.) questionnaires will be administered to patients at the baseline visit and at each follow up clinic visit. Both of these standardized function questionnaires are well validated and widely accepted in the literature.
9. **Hospital length of stay and readmission:** We will record the length of each patient's hospital stay and any readmission to our hospital for the 12-month duration of study.
10. **Infection:** Patients will have standard follow up clinic appointments at 1 and 4 months after surgery, at which time the clinical presence of possible wound drainage and periprosthetic infection will be evaluated. Patients will be followed up to 1 year after surgery to monitor for latent infections.

Table 1: Outcome measure and data collection schedule

	Pre-operative clinic visit	Each inpatient day	7 day app usage	2 week app usage	1 month clinic visit	4 month clinic visit	12 month clinic visit
Consent, Enrollment, Randomization	X						
Pain assessment	X	X	X		X	X	X
Opioid usage		X					
Pain medication log			X	X			
Knee swelling	X	X			X	X	
Knee ROM	X	X			X	X	X
Physical therapy milestones		X					
Nausea/vomiting		X	X				
Blood glucose	X	X					
Postoperative infection/Wound drainage		X			X	X	X
Length of stay		X					
KOOS, Jr. and SF-12	X				X	X	X

Consent Process

Patients will be asked to participate in the study at a preoperative clinic visit. The risks, benefits and the optional nature of the study will be emphasized. Patients may withdraw from the study at any given time. Consent will be obtained from one or more of the following three people: the attending surgeon, the orthopaedic surgery resident, or the research coordinator.

Participant Selection

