A subject key listing name, medical record number (MRN), age, sex, and study number will be kept in electronic format on a password-protected, encrypted computer, as well as in the research binder stored in a secure locked file cabinet. Data will be collected on paper case report forms (CRFs) and using the smart device application. The CRFs will not have any identifiable subject information, only the study number and subject's initials. Data will be entered into REDCap, a secure, web based application for building and managing online surveys and databases, by a study team member. The database will be made available to all investigators electronically. Data analysis will be performed by the investigators on a password-protected computer.

Each subject's safety will be monitored by his/her physician/investigator as the study procedures are performed and follow-up visits are conducted. Information regarding complications and adverse events will be gathered at each of the study follow-up visits. During administration of the study drug or placebo, all patients will be under close monitoring by the anesthesia and/or nursing staff. Any difference in risk of infection between study groups will be assessed, and this data will be reported to the Emory IRB as necessary. We will also monitor for and report any adverse outcomes and report to the Emory IRB as necessary. Patients will be followed out to one year after surgery to ensure that the intervention is safe. Notification to the Emory IRB will be done according to the IRB's specific procedures.

No patient will be enrolled in the study and have any study-related procedures performed, including completing subject clinical assessments, before an approved Informed Consent Document is signed.

References

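### Apart from glucose, nausea/vomiting and infection/wound drainage, no adverse event is scheduled for recording between dosing and the 1-month visit, and no by-arm summary of such events is planned

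*Combined protocol and SAP*

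**What the plan says.** The Data Safety and Monitoring Plan states when harms in general are collected: "Information regarding complications and adverse events will be gathered at each of the study follow-up visits". Data Collection lists the sources of data and names the hospital stay as one source and the "routine postoperative follow up visits (1 month, 4 months, and 12 months" as another, so the follow-up visits are not inpatient days.

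Under Therapeutic Intervention, the first dose is given shortly before surgery. For the second: "The second dose will be administered eight hours after the first dose in the inpatient setting by the nurse in that unit".

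Three kinds of harm are scheduled in hospital. Blood glucose is taken "at POD 1 and at each subsequent in-hospital POD using a hemocue". Emesis and antiemetic use are recorded, and nausea is logged in the app for 7 days. Table 1 marks "Postoperative infection/Wound drainage" for each inpatient day and for the three clinic visits. Table 1 has no row for adverse events or complications in general.

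The safety section also describes oversight: "Each subject's safety will be monitored by his/her physician/investigator as the study procedures are performed and follow-up visits are conducted", and "During administration of the study drug or placebo, all patients will be under close monitoring by the anesthesia and/or nursing staff". It adds that "Any difference in risk of infection between study groups will be assessed" and that other adverse outcomes will be reported to the IRB when needed. Exclusion criterion 11 removes from the study any patient whose complicated course leads to transfer to the ICU or to another facility.

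**The concern.** Exposure is brief and falls entirely in the perioperative period, so acute effects of the drug would be expected mainly during the hospital stay. The general adverse-event rule starts at the 1-month visit. An in-hospital complication outside the three scheduled items enters the trial data only if someone retrieves it later, and the plan does not say who does so or from what source.

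The plan follows patients for a year to establish safety, and it presents the comparison of two doses as one of its contributions. A reader of the results will want complications by dose. Short-lived inpatient events that are never recorded cannot appear in that table, and the six-monthly review under Adverse Event Reporting can use only what has been recorded. Patients with the most serious courses are the likeliest to be removed under criterion 11, possibly before any adverse-event collection takes place.

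**Working it through.** No figure in the plan bears on this point, so the check compares the schedule, the dosing and the analysis text.

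1. **Dosing window.** The second dose comes 8 hours after the first (Therapeutic Intervention).
2. **First general adverse-event collection.** This is the 1-month visit (Data Safety and Monitoring Plan, read with Data Collection). Taking a month as about 30 days, it comes about 30 days after dosing. A patient who misses that visit has the next scheduled collection at 4 months, and then at 12 months.
3. **Table 1 count.** The table has 12 rows. Nine carry a mark for each inpatient day: pain, opioid usage, swelling, range of motion, therapy milestones, nausea/vomiting, glucose, infection/wound drainage and length of stay. Three of the nine are direct harm items (nausea/vomiting, glucose, infection/wound drainage). Rows for adverse events in general: 0 of 12.
4. **Monitoring against recording.** The text on staff and investigator monitoring names no form, field or time point. Elsewhere the plan is explicit when it wants ward observations recorded: the Nausea/Vomiting Assessment item assigns emesis to the nurse to record. Monitoring alone therefore does not establish a trial record.
5. **Comparison by arm.** Statistical Analysis puts glucose in the mixed model by treatment group and time, with pairwise tests. It also says, in general terms, that differences in the primary and secondary outcomes will be determined. The secondary outcomes include nausea/vomiting, readmission, infection and wound drainage. The safety section adds infection. No section describes a definition, grading or by-arm summary for any other adverse event.
6. **Removed patients.** Criterion 11 does not say whether adverse events are still collected for a patient who is removed. If removal ends follow-up, that patient never reaches a 1-month collection, and no discharge or transfer record is specified in its place.

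**The case against.** The strongest reply is that the harms the protocol itself names for this drug are covered. It raises infection and wound healing in the background and hyperglycemia under Blood Glucose Levels, and it collects these prospectively in hospital, along with nausea and vomiting. It also records abandoned therapy sessions with the reason, length of stay and readmission. The investigator is named as monitoring safety during study procedures, and reporting to the IRB presupposes some record. This is a single-site trial, so the inpatient chart remains available at the 1-month visit, and gathering information then need not mean relying on the patient's memory.

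Much of this stands, and it rules out two stronger readings. A reader might infer that no in-hospital harm is collected until a month later. Table 1 contradicts that for three items. A reader might also infer from the safety section that infection is the only harm compared between arms. Statistical Analysis contradicts that for glucose explicitly, and for the other listed secondary outcomes in general terms, although it names no test for the binary ones.

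The reply does not cover the remaining events. Bedside monitoring and IRB reporting when needed set neither a routine inpatient record nor a tabulation. The plan does not exclude chart review, but it does not provide for it either, so capture may differ between patients.

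**Conclusion.** The point holds in limited form. For complications other than glucose, nausea/vomiting and infection/wound drainage, the plan schedules no recording between dosing and the 1-month visit, a gap of about 30 days that contains the whole exposure period. It plans no by-arm summary of these events, and patients removed on transfer may leave no adverse-event record. This rests on reading the follow-up visits as the clinic visits at 1, 4 and 12 months, as Data Collection defines them, and on there being no separate adverse-event form outside these documents.

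The number of events affected cannot be estimated. The documents give no expected rates for such events and no likely share recovered at 1 month. A reader might want to express the gap as lost power, but the plan proposes no test on these events and the sample size was set for pain, so such a figure would rest wholly on assumptions.

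The primary outcomes and the listed secondary outcomes are unaffected. This is a cheap improvement to the safety data, and inpatient events that were not noted at the time may be hard to recover reliably later.

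**What to change.** - Add an *Adverse events/complications* row to Table 1, marked for each inpatient day and for the 1, 4 and 12 month visits.
- In the Data Safety and Monitoring Plan, change the timing of collection to *during the hospital stay and at each follow-up visit*.
- Have the blinded study team abstract inpatient complications from the chart onto a CRF page at discharge or transfer, including for patients later removed under criterion 11.
- Add to Statistical Analysis a table of the number of patients with each type of event by randomised arm, with in-hospital and post-discharge events shown separately.

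The cost is one table row, one CRF page, one amended sentence, one output table and a little chart-abstraction time per patient. Inpatient data are already collected daily. No extra test, visit or change to treatment is involved.
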